**Table 8 National Cancer Institute common terminology criteria for grading diarrhoea adverse events**

Adverse Event Grade	Diarrhoea
1	Increase of <4 stools/day over baseline; mild increase in ostomy output compared to baseline
2	Increase of 4-6 stools/day over baseline; moderate increase in ostomy output compared to baseline;
3	Increase of $\geq 7$ stools/day over baseline; incontinence; hospitalisation indicated; severe increase in ostomy output compared to baseline; limiting self care activities of daily living
4	Life-threatening consequences; urgent intervention indicated
5	Death

Data will be recorded by the investigators in the eCRF at each study visit and by subjects in the DMD every week and in the FACIT-D every 3 weeks. These are considered to be independent sources of study data, and investigators must not use information collected in the DMD and FACIT-D to supplement data entry into the eCRF. Where comparable data are collected in the eCRF and in the DMD, secondary endpoints will be evaluated to contrast and compare these data within each treatment group, although differences between the eCRF data and the PRO data will preclude formal comparisons.

All subjects will complete the baseline DMD and the FACIT-D during the 3 days prior to randomisation, before any study-related treatment is administered. Subjects randomised to receive octreotide will complete a second baseline DMD and the FACIT-D before starting the first cycle of treatment with lapatinib and capecitabine. Hence, subjects randomised to receive octreotide will complete the baseline DMD and the FACIT-D (Week -1) prior to receiving the first dose of octreotide (0.1mg subcutaneous tolerability test dose), and all subjects will complete the baseline DMD and the FACIT-D prior to receiving the first dose of lapatinib and capecitabine (Week 0).

The DMD will be completed every week after the first dose of lapatinib and capecitabine is administered (Week 1, Week 2, Week 3, etc), until the end of study visit (Week 24, disease progression, unacceptable toxicity or subject withdrawal if this is sooner). The FACIT-D will be completed every 3 weeks during treatment with lapatinib and capecitabine (Week 3, Week 6, Week 9, etc), until the end of study visit (Week 24, disease progression, unacceptable toxicity or subject withdrawal if this is sooner). The DMD and FACIT-D will not be completed beyond 24 weeks of treatment.

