### **4.3. Permanent Discontinuation from Study Treatment and Subject Completion Criteria**

#### **4.3.1. Discontinuation from Treatment with Octreotide**

Subjects randomised to receive octreotide must be given one 0.1mg dose of the standard formulation of octreotide s.c. to assess tolerability at least one hour before the first dose of the LAR formulation is administered. Subjects who show any evidence of intolerability to octreotide administered s.c. **must not** receive treatment with the LAR formulation; these subjects should receive treatment with lapatinib and capecitabine and should not be withdrawn from the study.

Subjects randomised to receive octreotide will be given prophylactic octreotide (Sandostatin LAR) 40mg 7 days before the start of treatment with lapatinib and capecitabine and again 28 days later. Episodes of mild diarrhoea which occur following treatment with octreotide LAR should be managed in accordance with the diarrhoea management guidelines ([Appendix 1](#)). The use of octreotide in the s.c. formulation for the management of diarrhoea refractory to treatment with loperamide is not excluded. Investigators should use their clinical judgement concerning the use of octreotide s.c. in

subjects randomised to receive treatment with octreotide LAR, particularly during Week 2 through to Week 12 of treatment with lapatinib and capecitabine, when circulating concentrations of octreotide should already be within the clinically effective range. Subjects who report constipation with a severity of NCI CTCAE Grade 2 and above (Table 9) or other adverse events which are considered likely to be related to octreotide treatment following the first dose of octreotide LAR must not receive the second dose of octreotide LAR, but should continue to receive lapatinib and capecitabine and should not be withdrawn from the study.

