### 7.1.4. Post-Randomisation

Subjects will be randomised to receive octreotide or to receive no octreotide.

For subjects randomised to receive octreotide:

- Administer the octreotide 0.1mg s.c. tolerability assessment dose, monitor for at least one hour and record any AEs associated with this dose.
- Administer first dose of octreotide 40mg LAR (only in subjects who have not shown intolerance to the octreotide 0.1mg s.c. tolerability assessment dose).

For subjects randomised to receive no octreotide:

- Dispense lapatinib and capecitabine to the subject with instructions for taking therapy.

All subjects will be given advice concerning the management of diarrhoea. It is recommended that subjects should be provided with loperamide for the prompt management of diarrhoea.

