#### **7.4.7. Time Period and Frequency of Detecting AEs and SAEs**

The investigator or site staff is responsible for detecting, documenting and reporting events that meet the definition of an AE or SAE.

AEs will be collected from the time of treatment with the first dose of octreotide for subjects randomised to receive octreotide and treatment with the first dose of lapatinib and capecitabine for subjects randomised to receive no octreotide until 30 days following the end of the 24 week study period or discontinuation of study-related treatment, whichever is sooner, regardless of initiation of a new cancer therapy or transfer to hospice.

Serious AEs will be collected over the same time period as stated above for AEs. In addition, any SAE assessed **as related** to study participation (e.g., protocol-mandated procedures, invasive tests, or change in existing therapy), study treatment or GSK concomitant medication must be recorded from the time a subject consents to participate in the study up to and including any follow-up contact. All SAEs will be reported to GSK within 24 hours, as indicated in Section 7.4.9.

Serious AEs, AEs of special interest, AEs leading to treatment discontinuation and pregnancies will be collected for all subjects who enter the LTFU phase of the study (Section 7.1.9).

After discontinuation of study treatment, the investigator will monitor all AEs/SAEs that are ongoing until resolution or stabilization of the event or until the subject is lost to follow-up. At any time after 30 days the investigator may report any AE that they believe possibly related to study treatment.

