1.1 Study design

This is a randomised, parallel group, multi-centre, open-label Phase II study in subjects with HER2-positive metastatic breast cancer which has progressed following prior therapy, which must have included anthracyclines and taxanes and therapy with trastuzumab in the metastatic setting. This study is not placebo controlled, and there is no active comparator.

Subjects must be screened for eligibility and informed consent must be given before any study-related procedures are conducted.

All subjects will receive treatment with lapatinib 1250mg once daily and capecitabine 1000mg/m² twice daily until disease progression. Lapatinib will be given every day; capecitabine will be given in 3 week cycles of two weeks treatment followed by one week off treatment. All subjects with episodes of diarrhoea will be encouraged to follow the diarrhoea management guidelines for subjects receiving lapatinib. One cycle of lapatinib and capecitabine equates to three study weeks.

Subjects will be randomised in a 1:1 ratio to receive either:

- Octreotide (Sandostatin long acting release (LAR)) 40mg 7 days before the start of treatment with lapatinib and capecitabine and again 28 days later, or

- No octreotide treatment.

For subjects randomised to receive octreotide, treatment with lapatinib and capecitabine will be initiated 7 days after the first dose of octreotide given as the LAR formulation. For subjects randomised to receive no octreotide, treatment with lapatinib and capecitabine will be initiated immediately following enrolment.

Subjects randomised to receive octreotide LAR must be given one 0.1mg dose of the standard formulation of octreotide subcutaneous (s.c.) to assess tolerability at least one hour before the first dose of the LAR formulation is administered. Subjects with significant intolerance to octreotide 0.1mg s.c. will not receive treatment with octreotide LAR, but will receive treatment with lapatinib and capecitabine as scheduled.

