2.1.3.2 Reference start date

There are three reference start dates:

- Age is an eligibility requirement and therefore the reference start date for age is the date of screening.
- The safety reference start date is the date of a subject receiving the first dose of study treatment (i.e., octreotide, lapatinib or capecitabine).
- The efficacy reference start date is the date of randomization and will be used to calculate study day for efficacy measures and baseline characteristics.

The reference start date for all other, non-safety assessments (i.e., tumor assessment, death, disease progression, tumor response, ECOG performance status, and patient reported outcomes (PRO)) is the date of randomization.

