2.2 Analysis Populations

Intent-to-Treat Population

The Intent-to-Treat (ITT) population will comprise all randomised subjects regardless of whether or not treatment was administered. This population will be based on the treatment to which the subject was randomised. Any subject who receives a treatment randomization number will be considered to have been randomised. The primary analysis of disease efficacy and all diarrhoea-related efficacy endpoints will be analysed using the ITT population.

Modified ITT

The modified ITT (m-ITT) population will comprise all subjects in the ITT population and under Octreotide arm this population will include subjects who do not show intolerance to octreotide in the s.c. formulation and who do not have non treatment related diarrhoea recorded

as an AE after the first dose of octreotide LAR and prior to the start of treatment with lapatinib and capecitabine. A sensitivity analysis of diarrhoea-related primary efficacy endpoint will be conducted using the m-ITT population.

Per Protocol Population

The Per-Protocol (PP) population will comprise all randomised subjects who receive at least one dose of study treatment and who comply closely with the protocol (that is subjects who are not excluded from PP set as per PDMP). The PP population will not be analysed if this population comprises more than 95% or less than 50% of the ITT population. The analysis of primary efficacy endpoint will be repeated using the PP population.

Subjects with potential PDs will be excluded from PP population based on Protocol Deviation Management Plan (PDMP).

Safety Population

The Safety population will comprise all randomised subjects who receive at least one dose of study treatment and will be based on the actual treatment received if this differs from that to which the subject was randomised. This population will be used for the analysis of clinical safety data. Moreover, if a subject who was randomised to Octreotide arm, showed intolerance to octreotide in the s.c. formulation, and took at least one dose of lapatinib or capecitabine, then subject will be included in no Octreotide arm for safety analysis.

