2.7 Safety analyses

Unless otherwise specified, all the safety analyses will be based on the Safety population and summaries will include all events or assessments collected during the study. All the summaries will be presented by treatment group.

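### A reaction to the octreotide s.c. test dose is counted under Lap+Cap in the safety tables when the intolerant subject goes on to lapatinib or capecitabine

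*SAP*

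**What the plan says.** SAP 2.2 groups the Safety Population by treatment actually received. It then adds a rule for a subject randomised to octreotide who is intolerant to the s.c. dose and takes at least one dose of lapatinib or capecitabine: "then subject will be included in no Octreotide arm for safety analysis".

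Going on to both drugs is the planned path for these subjects. Protocol 4.3.1 says "these subjects should receive treatment with lapatinib and capecitabine and should not be withdrawn from the study", and SAP 1.1 says that subjects with significant intolerance "will not receive treatment with octreotide LAR, but will receive treatment with lapatinib and capecitabine as scheduled".

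Reactions to the test dose are study data. Protocol 7.1.4 instructs sites: "Administer the octreotide 0.1mg s.c. tolerability assessment dose, monitor for at least one hour and record any AEs associated with this dose". Protocol 7.4.7 states that "AEs will be collected from the time of treatment with the first dose of octreotide for subjects randomised to receive octreotide". Protocol section 2 identifies that first dose as the test dose, since the Week -1 questionnaires are completed "prior to receiving the first dose of octreotide (0.1mg subcutaneous tolerability test dose").

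For the tables, SAP 2.7 says "summaries will include all events or assessments collected during the study", presented by treatment group. SAP 2.1.3.2 defines the safety reference start date as "the date of a subject receiving the first dose of study treatment (i.e., octreotide, lapatinib or capecitabine").

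**The concern.** The test dose is there to reveal intolerance to octreotide. The rule in SAP 2.2 takes the subjects in whom it does so and places everything that happened to them, including the reaction itself, in the column labelled as having no octreotide. At the time of the reaction the subject has received octreotide and nothing else, so this conflicts with the as-treated principle in the same paragraph.

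The direction is fixed: each such event leaves the octreotide column and enters the comparator. Safety and tolerability is a secondary objective (Protocol Table 7), and octreotide is the only drug that SAP 2.1.3.1 calls investigational. Protocol 9.3.1 has the as-treated definition without this reassignment, and SAP section 4 does not list it as a change.

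**Working it through.** The plan gives no figure for this rule, so the check is to follow one event through the text and then illustrate its size.

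**Following the event**

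1. A subject randomised to octreotide has a reaction to the s.c. test dose. It is recorded as an AE (Protocol 7.1.4) and falls inside the collection period (Protocol 7.4.7).
2. She does not receive LAR and starts lapatinib and capecitabine. SAP 2.2 now places her in Lap+Cap for safety.
3. No date rule removes the reaction from the main AE tables. The safety reference date and the on-treatment window (SAP 2.1.3.2 and 2.1.3.10) both open at the first dose of any component, octreotide included. SAP 2.7 in any case takes all events collected.
4. The reaction is counted under Lap+Cap in the SOC/PT table of all AEs (SAP 2.7.2) and, if serious, in the SAE tables (SAP 2.7.2 and 2.7.4). If judged related, it is also counted in the related-AE table, because relatedness is to study treatment as a whole. None of these tables has an incidence threshold.

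**Size**

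Inputs: 62 enrolled (SAP section 1) and 1:1 allocation. Assumptions: 31 per arm, and *k* moved subjects with one test-dose event each. For a term otherwise absent:

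- as randomised: *k*/31 - 0/31
- under SAP 2.2: 0/(31 - *k*) - *k*/(31 + *k*)

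| *k* | As randomised, octreotide minus Lap+Cap | Under SAP 2.2 |
|---|---|---|
| 0 | 0 | 0 |
| 1 | 1/31 - 0/31 = +3.2 points | 0/30 - 1/32 = -3.1 points |
| 2 | 2/31 - 0/31 = +6.5 points | 0/29 - 2/33 = -6.1 points |

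For a common term, take nausea with one moved subject whose only nausea was at the test dose. The protocol gives two rates for lapatinib with capecitabine: 29% (Table 3) and 47% (Table 2).

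| Background rate | Events per arm | As randomised | Under SAP 2.2 |
|---|---|---|---|
| 29% | about 9/31 | 10/31 - 9/31 = +3.2 | 9/30 - 10/32 = 30.0 - 31.25 = -1.3 |
| 47% | about 15/31 | 16/31 - 15/31 = +3.2 | 15/30 - 16/32 = 50.0 - 50.0 = 0.0 |

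**Tables with a threshold**

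- The non-serious disclosure table (SAP 2.7.6) requires more than 5%. Taken by arm, one subject is 1/32 = 3.1% and two are 2/33 = 6.1%.
- The maximum-grade table (SAP 2.7.2) requires 5% of all subjects: 3/62 = 4.8% falls short and 4/62 = 6.5% passes.
- A term that is already common passes both.

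**The case against.** The strongest reply is that these subjects belong with Lap+Cap. They never receive LAR, SAP octreotide compliance and exposure count LAR only (2.4.1 and 2.7.1.1), and the s.c. half-life is about 100 minutes (Protocol 1.3.1), so five half-lives is 500 minutes, or 8.3 hours. That stands for events after lapatinib and capecitabine begin. It does not justify placing a reaction to octreotide itself in the comparator column.

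The second reply is that the reach is small. There may be no intolerant subjects, the safety tables are descriptive, the report is abbreviated after a futility stop, and the AE listing and the listing of analysis populations let a reader trace a moved subject. All of this is true and limits the importance. Listings do not correct the tables, however. SAP 2.7.5 also tabulates AEs that led to octreotide being stopped, but the SAP does not say whether withholding LAR counts as stopping. If it does, that table too would show the reaction under Lap+Cap.

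Three narrower points also stand:

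- The sign reversal for nausea depends on the background rate. At 47% the true excess is erased, not reversed.
- If the subject has nausea again on lapatinib and capecitabine, she counts for the term under Lap+Cap anyway, and the test-dose event adds nothing to that column.
- SAP 2.7.6 refers to treatment-emergent events without defining them, so the handling of this event in the disclosure tables is less certain than in the tables of SAP 2.7.2.

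**Conclusion.** The concern holds. Applied as written, SAP 2.2 and 2.7 count a reaction to the octreotide test dose under Lap+Cap whenever the subject goes on to lapatinib or capecitabine. The defect is confined to the interval from the test dose to the first dose of either drug; grouping these subjects with Lap+Cap afterwards is defensible.

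With 31 per arm assumed, one moved subject shifts the between-arm difference by about 6.4 points for a term otherwise absent (+3.2 to -3.1). The shift is 3.2 to 4.5 points in the nausea examples (+3.2 to 0.0, or to -1.3). With no intolerant subjects there is no effect, and the documents do not give their number. ITT efficacy and events after LAR are untouched. The rule should be corrected, but the primary result does not depend on it.

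**What to change.** Amend the reassignment sentence in SAP 2.2 as follows:

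- Tabulate AEs with onset from the s.c. test dose until the first dose of lapatinib or capecitabine under octreotide, with all subjects given any octreotide (s.c. or LAR) as the denominator.
- Let the reassignment to Lap+Cap stand for AEs with onset after lapatinib or capecitabine starts, and footnote the moved subjects.
- State that an event in the earlier window is not also counted under Lap+Cap in the whole-study tables, including the row for any event and the disclosure tables.
- State how partial AE start dates are assigned, because SAP 5.1.1 can impute them to the study treatment start date.
- Record the rule in SAP section 4.

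Under the same assumptions, one moved subject would then appear as 1/31 = 3.2% under octreotide in that window and not at all under Lap+Cap.

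The cost is one amended sentence and one extra table or split by AE onset date. No new data are needed, since test-dose AEs and octreotide administration are already recorded (Protocol 7.1.4 and 5.8). There are two drawbacks. A moved subject appears under octreotide for one period and Lap+Cap for the next, which the footnote must explain. For subjects who tolerate the test dose, the window also contains the seven days after LAR, so the table shows early octreotide events in general and does not isolate test-dose reactions.

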## 9.3. Data Analysis Considerations

### 9.3.1. Analysis Populations

The Intent-to-Treat (ITT) population will comprise all randomised subjects regardless of whether or not treatment was administered. This population will be based on the treatment to which the subject was randomised. Any subject who receives a treatment randomisation number will be considered to have been randomised. The primary analysis of disease efficacy and all diarrhoea-related efficacy endpoints will be conducted using the ITT population.

The modified ITT (m-ITT) population will comprise all subjects in the ITT population who do not show intolerance to octreotide in the s.c. formulation and who do not have diarrhoea recorded as an AE after the first dose of octreotide LAR and prior to the start of treatment with lapatinib and capecitabine. The supplementary analysis of all diarrhoea-related efficacy endpoints will be conducted using the m-ITT population.

The Per-Protocol (PP) population will comprise all randomised subjects who receive at least one dose of study treatment and who comply closely with the protocol. Major protocol violations that would exclude subjects from the PP population will be defined and documented in the Reporting and Analysis Plan (RAP) prior to database release. The PP population will not be analysed if this population comprises more than 95% of the ITT population.

The Safety population will comprise all randomised subjects who receive at least one dose of study treatment and will be based on the actual treatment received if this differs from that to which the subject was randomised. This population will be used for the analysis of clinical safety data.

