2.7.1.1 Octreotide

The number and percentage of subjects who received a given number of infusions of octreotide (an infusion is defined as one dose of 20mg, patients should have two 20 mg infusions per dose) (0, 1, 2, 3, 4, >4 20mg infusions) will be reported. The duration of exposure to study treatment in days, calculated as (last dose of octreotide – first dose of octreotide +1), will also be summarised.

Dose intensity (total dose delivered i.e. two 20 mg infusions per dose) will be summarized using mean, median, standard deviation, minimum, and maximum.

The number of subjects with dose reductions, dose escalation, dose delays or missed doses will be summarized using frequency and percentages.

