2.7.2 Adverse events (AEs)

AEs will be graded by the investigator according to the NCI-CTCAE, Version 4.03. Adverse events will be coded to the PT level using Medical Dictionary for Regulatory Activities (MedDRA).

The following adverse event summaries will be produced by treatment group: overview of adverse events and deaths (number and % of subjects who died, any AE, any SAE, any dose reductions/interruptions, AEs related to study treatment, SAEs related to study treatment, AEs leading to treatment discontinuation, AEs requiring additional therapy, AEs leading to withdrawal), AEs by SOC and PT summarized by relationship (all AEs and AEs related to study treatment), SAEs by SOC and PT.

A summary of all AEs that occurred in strictly 5% or higher of all the subjects will be provided (no rounding for the percentage will be used in terms of 5% threshold, e.g., event with 4.9% incidence rate should not be included in this table). The summary will be displayed by preferred term (PT) and maximum grade.

The summary will use the following algorithms for counting the subject:

- **Preferred term row:** Subjects experiencing the same AE preferred term several times with different grades will only be counted once with the maximum grade.
- **Any event row:** Each subject with at least one adverse event will be counted only once at the maximum grade no matter how many events they have.

These summaries are displayed in descending order of Octreotide+Lap+Cap group by SOC and PT. In the SOC row, the number of subjects with multiple events under the same system organ class will be counted once.

A study treatment-related AE is defined as an AE for which the investigator classifies the relationship to study treatment as “Yes”. A worst case scenario approach will be taken to handle missing relatedness data, i.e., the summary table will include events with the relationship to study treatment as ‘Yes’ or missing. The summary table will be displayed in descending order of Octreotide+Lap+Cap group by SOC and PT

A listing for all AEs will be provided including seriousness, relatedness, action taken.

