2.7.6 Clinical Trial Safety Disclosure

For the legal requirements of ClinicalTrials.gov and EudraCT, two required tables on treatment emergent adverse events which are not serious adverse events with an incidence greater than 5% and on treatment emergent serious adverse events and SAE suspected to be related to study treatment will be provided by system organ class and preferred term on the safety set population.

If for a same patient, several consecutive AEs (irrespective of study treatment causality, seriousness and severity) occurred with the same SOC and PT:

a single occurrence will be counted if there is ≤ 1 day gap between the end date of the preceding AE and the start date of the consecutive AE

more than one occurrence will be counted if there is > 1 day gap between the end date of the preceding AE and the start date of the consecutive AE

For occurrence, the presence of at least one SAE / SAE suspected to be related to study treatment / non SAE has to be checked in a block e.g., among AE's in a ≤ 1 day gap block, if at least one SAE is occurring, then one occurrence is calculated for that SAE.

The number of deaths resulting from SAEs suspected to be related to study treatment and SAEs irrespective of study treatment relationship will be provided by SOC and PT.

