3.3 Sample Size Re-estimation

Sample size re-estimation is not planned for this study.

4 Change to protocol specified analyses

Since final CSR will be an abbreviated CSR, not all endpoints will be analysed. [Table 1-3](#) contains reduced list of endpoints as compared to protocol.

Secondary endpoint Patient reported Diarrhoea Management Diary (DMD) is reported using a listing of patients reporting changes in bowel movements from baseline (frequency and/or consistency), recorded in the DMD.

5 Appendix

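### The SAP's safety population moves patients who reacted to the octreotide test dose into the no-octreotide arm, so their octreotide reactions are tabulated under control

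*SAP*

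**What the plan says.** Protocol 9.3.1 says the Safety population "will be based on the actual treatment received if this differs from that to which the subject was randomised", and it makes no exception for intolerance of the test dose. SAP 2.2 repeats that rule and adds one. If a patient randomised to octreotide showed intolerance to the subcutaneous formulation and took at least one dose of lapatinib or capecitabine, "then subject will be included in no Octreotide arm for safety analysis".

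Other provisions decide what this does to the tables:

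- Protocol Section 2 treats the test injection as octreotide treatment. Baseline questionnaires come before "the first dose of octreotide (0.1mg subcutaneous tolerability test dose".
- Protocol 7.1.4 tells sites to give the test dose, "monitor for at least one hour and record any AEs associated with this dose". Protocol 7.4.7 starts adverse event collection in this arm at the first octreotide dose.
- SAP 2.1.3.2 sets the safety reference date at the first dose of octreotide, lapatinib or capecitabine.
- SAP 2.7 bases the safety summaries on every event collected during the study and shows them by treatment group. The two registry tables in SAP 2.7.6 "will be provided by system organ class and preferred term on the safety set population".
- SAP Section 4, on changes from the protocol, says that Table 1-3 "contains reduced list of endpoints as compared to protocol" and that the diary endpoint becomes a listing. It does not mention the new safety-arm rule.

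**The concern.** The test dose is there to find patients who cannot tolerate octreotide. Protocol 1.3.1 expects it to reveal hypersensitivity, which it names as the only contraindication. The SAP rule takes these patients out of the octreotide column and adds them to control, so any distortion from test-dose reactions favours octreotide.

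The move is also the expected course. Protocol 3.1 has intolerant patients start lapatinib and capecitabine on schedule, which meets the rule's condition. A patient who reacts and stops before either drug stays under octreotide, so the column that receives a reaction depends on what the patient does afterwards.

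At stake are the by-arm adverse event and serious adverse event tables, which remain a secondary endpoint in the reduced SAP (Table 1-3), and the registry tables. If a reaction is recorded as the reason octreotide was stopped, the SAP 2.7.5 table of events leading to octreotide discontinuation would show it in the arm labelled as having no octreotide.

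**Working it through.** **Text check.** The plan states no figure to reproduce, so the check starts with the rules in sequence.

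1. Intolerance to the test dose implies the test dose was given, so the patient received octreotide.
2. The resulting adverse event is recorded (Protocol 7.1.4, 7.4.7).
3. The event falls on or after the safety reference date (SAP 2.1.3.2) and within the events summarised (SAP 2.7).
4. The patient's arm in those summaries is Lap+Cap (SAP 2.2).
5. Nothing in the SAP excludes test-dose events of moved patients or shows them separately in the summary tables.

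The octreotide reaction is therefore counted in the control column.

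**Illustration of size.** SAP Section 1 gives 62 enrolled. Everything else here is an assumption: a 31:31 split, *k* moved patients with one test-dose event each, *m* tolerant octreotide patients who also have a test-dose event, and no such events in control.

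- True difference (octreotide minus control) = (*k* + *m*)/31 - 0/31
- Tabulated difference under SAP 2.2 = *m*/(31 - *k*) - *k*/(31 + *k*)

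| *k* | *m* | True | Tabulated |
|---|---|---|---|
| 1 | 0 | 1/31 = +3.2 | 0/30 - 1/32 = -3.1 |
| 2 | 0 | 2/31 = +6.5 | 0/29 - 2/33 = -6.1 |
| 3 | 0 | 3/31 = +9.7 | 0/28 - 3/34 = -8.8 |
| 2 | 1 | 3/31 = +9.7 | 1/29 - 2/33 = -2.6 |
| 3 | 2 | 5/31 = +16.1 | 2/28 - 3/34 = -1.7 |
| 1 | 1 | 2/31 = +6.5 | 1/30 - 1/32 = +0.2 |
| 2 | 2 | 4/31 = +12.9 | 2/29 - 2/33 = +0.8 |
| 3 | 3 | 6/31 = +19.4 | 3/28 - 3/34 = +1.9 |

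(Differences in percentage points.)

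The tabulated sign reverses when *m* < *k*(31 - *k*)/(31 + *k*). That bound is 30/32 = 0.94 for *k* = 1, 58/33 = 1.76 for *k* = 2 and 84/34 = 2.47 for *k* = 3. In whole patients, reversal therefore needs *m* < *k*.

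Tabulated minus true, as *m* runs from 0 to 4, is -6.4 to -5.9 points for *k* = 1, -12.5 to -11.6 for *k* = 2 and -18.5 to -17.1 for *k* = 3. Each moved patient lowers the tabulated difference by about 6 points (5.7 to 6.4).

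The assumed split matters little. For *k* = 1 and *m* = 0, 29 octreotide v 33 control gives +3.4 true and -2.9 tabulated; 33 v 29 gives +3.0 and -3.3.

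**The case against.** The case for the rule is that the octreotide arm is defined by two 40mg LAR injections. The test dose is one small, short-acting injection, with a half-life of about 100 minutes (Protocol 1.3.1). An intolerant patient gets no LAR and from then on is treated like a control patient. SAP 2.7.1.1 takes the same view of exposure, counting octreotide only in LAR units: "an infusion is defined as one dose of 20mg, patients should have two 20 mg infusions per dose". Control patients may also receive subcutaneous octreotide as rescue, so subcutaneous exposure alone cannot define the arm. Keeping intolerant patients under octreotide would place up to 24 weeks of lapatinib and capecitabine toxicity, without LAR, in the octreotide column, and that toxicity is heavy: 69% had diarrhoea in EGF100151 (Protocol Table 2).

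The effect may also be small or nil. Octreotide is described as generally well tolerated. The table of events by preferred term and grade needs 5% of all patients, so three events in 62 (3/62 = 4.8%) would not appear. The registry table of non-serious events also has a 5% threshold. A patient counted once per preferred term may be counted anyway for events common on lapatinib and capecitabine. The cases stay traceable, since "A listing for all AEs will be provided including seriousness, relatedness, action taken", and no safety test is planned.

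Much of this stands. It explains why later follow-up might sit with control, and it limits which table rows are affected. It does not justify counting a reaction to octreotide against the arm that is labelled as not having had it. The tables by system organ class and preferred term, the serious event tables including the registry one, and the octreotide-discontinuation table carry no threshold. Listings let a reader find the cases but do not correct the summaries.

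**Conclusion.** The concern holds. SAP 2.2 departs from its own actual-treatment principle and from Protocol 9.3.1, the departure is not declared in SAP Section 4, and following it books octreotide reactions under control.

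The size is unknown because the documents do not give the number of moved patients. With none there is no effect. Under the illustrative assumptions, each moved patient shifts the tabulated difference in test-dose events by about 6 points towards octreotide. That reverses the sign when fewer tolerant patients react than are moved, and nearly removes the difference when the two numbers are equal. These figures depend on the assumed 31:31 split, one event per moved patient and no such events in control. For *k* above 1 they apply to test-dose events pooled together, or to a single term only if all the patients share it. Only the safety tables are affected; the primary analysis is by randomised arm.

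**What to change.** Replace the last sentence of the Safety population definition in SAP 2.2 with:

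> A subject randomised to octreotide who received the 0.1mg s.c. test dose or any LAR dose is analysed in the Octreotide+Lap+Cap arm. A subject randomised to octreotide who received neither, but took lapatinib or capecitabine, is analysed in the Lap+Cap arm. Rescue s.c. octreotide does not change the arm.

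Add a listing of patients who had the test dose but no LAR, and repeat the adverse event overview without them. The repeat deals with the downside of the change, which is that their follow-up on lapatinib and capecitabine without LAR would sit in the octreotide column.

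The cost is one sentence, one listing and one repeated table. No new data and no protocol amendment are needed.
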